8.2 Subject disposition

Subject disposition information will be summarized by treatment group and overall. The number and percent of subjects who are randomized, who are randomized as replacement, who complete the study and who withdraw early from the study will be presented.

The primary reason for early withdrawal will also be tabulated.

The number of subjects randomized will be used as the denominator for the percentage calculation.

The number and percent of subjects in each analysis set and the mITT CT & GC analysis eligible subjects will also be tabulated.

Subject disposition will be listed.

8.3 Protocol deviations

The number of patients excluded from ITT, mITT, Safety analyses sets and reasons for exclusion will be summarized by treatment group and overall. Similarly, summaries of CT & GC analysis eligible patients within mITT will be presented with reasons for exclusion summarized by treatment group and overall.

All protocol deviations identified will be summarized by treatment group and overall.

A listing will include the inclusion/exclusion criteria violated at Screening and Enrollment Visits as well as other protocol deviations identified.

8.4 Demographics and baseline characteristics

Continuous measures (e.g., age, race, ethnicity, height, weight, BMI, vital signs, etc.) will be summarized treatment group and overall using descriptive statistics (n, mean median, standard deviation, 25th percentile, 75th percentile, min, and max). Meanwhile, categorical baseline characteristics will be summarized by treatment group and overall using frequency counts and percentages. All demographic & baseline information will also be in subject-level listings.

8.5 Medical history

A summary of medical/surgical/gynecologic/sexual health history will be presented by system organ class (SOC) and preferred term (PT) using Medical Dictionary for Regulatory Affairs® (MedDRA) Version 20.1 or higher. Medical history will be listed.

8.6 Concomitant medications

Concomitant medications will be assessed and includes any medication that would be taken during the study including all over the counter medications, vitamins and nutritional supplements.

Medications used in this study will be coded by using WHO drug dictionaries.

Concomitant medications will be summarized descriptively using frequency tables by ATC class and preferred name by treatment group. Concomitant medications will be listed.

8.7 Treatment adherence

Adherence with AMPHORA gel usage during study (rate of product use adherence) is defined using the gel applicators and e-diary data. Specifically, adherence will be determined using 2 methods. Method 1: adherence = # of times product is properly used as noted in the e-diary / # of coital events noted during the treatment phase in the e-diary. Method 2: adherence = # of times product is used as determined by Trypan Blue staining / # of coital events during the treatment phase noted in the e-diary. Summary statistics of adherence by method will be presented overall and by treatment group.

Study product adherence will be calculated as: $100 \times [\text{adherence ratio calculated via Method 1 (or 2)}]$. The maximum percentage of doses used will be 100%.

Study drug compliance, times of product use (determined via e-diary & dye staining), and times of coital event will be summarized by treatment group by the number of subjects (n), mean, std dev, std error, median, min, and max.

Study drug compliance will be summarized in categories “ $\geq 20\%$ ”, “ $\geq 40\%$ ”, “ $\geq 60\%$ ”, “ $\geq 80\%$ ”, and “100%” using frequency tables. For the purposes of the frequency table, each compliance group will be deemed mutually exclusive (e.g., compliance rate of 41% would be in the $\geq 40\%$ category only and would not be counted in the $\geq 20\%$ category).

Treatment compliance data will be listed.

8.8 Efficacy analyses

This section addresses separately the analyses to be conducted on the primary, secondary and exploratory efficacy endpoints.

8.8.1 Analysis of primary efficacy endpoint

The primary objective of this trial is to demonstrate the efficacy of AMPHORA compared to placebo for the prevention of urogenital CT infection. The primary efficacy endpoint is the proportion of subjects who experience at least one urogenital CT infection during the study intervention period (incident infection of CT).

The primary statistical hypothesis being tested is that: There is no difference in the proportion of subjects with CT infections in the AMPHORA intervention group versus placebo. In statistical terms:

$H_0: p_{\text{AMPHORA}} = p_{\text{placebo}}$, $H_A: p_{\text{AMPHORA}} \neq p_{\text{placebo}}$

where p_{AMPHORA} and p_{placebo} denote the proportion of subjects with CT infections during the study in the AMPHORA and placebo groups, respectively.

Denominators for each proportion are the number of subjects in the mITT population in each intervention group’s analysis eligible subset. To test for superiority over the placebo, the incidence of infection of CT will be compared against placebo based on a Chi-Square test. The estimate of difference in proportions, 95% confidence interval and p-value will be presented. A two-sided 5% type I error rate ($\alpha=0.05$) will be used. Note: for a subject to be considered re-infected with CT any positive NAAT test during the treatment phase (visits 1-5) will constitute re-infection. For a subject to be considered not re-infected, a subject with a negative NAAT at visits 1 & 5 with no positive NAATs in between is deemed not re-infected.

As a complementary analysis, tables will be created which also summarize re-infection by each scheduled visit.

CT infection information will be listed.

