# 1 Background Information and Scientific Rationale

# 1.1 Background Information

Chlamydia trachomatis (CT) infection remains the most frequently reported infectious disease in the United States (US) (1). Several sequelae can result from CT infection in women, the most serious of which include pelvic inflammatory disease (PID) and scarring of the fallopian tubes, ovaries, endometrial lining, and occasionally, adjacent perineum, which increases the risk of future ectopic pregnancy and tubal infertility. These consequences are the main reason that CT infection is estimated to be the costliest of all non-viral sexually transmitted infections (STIs) (2).

An acidic vaginal pH and colonization with *Lactobacillus* species (LB) are two proven components of the multiple defense mechanisms active against infection in the lower female genital tract (3). These species are thought to play key protective roles by producing various bacteriostatic and bactericidal compounds (4), (5), (6). A lower vaginal pH may inhibit STIs, including CT infection (7). In vitro studies have shown that exposure to vaginal secretions at lower pH significantly inhibits CT replication (7), (8). In another experiment, the growth of CT within epithelial cells was inhibited by acidic pH (9).

A prospective case-controlled study found an association between CT infection and higher vaginal pH (median pH of 4.5 in CT and 4.0 in controls, respectively), independent of any other factors (10). The study included 144 cases of CT infections and 145 controls. Sixty-two (62) of the women with CT were diagnosed with concurrent STIs (bacterial vaginosis [BV], genital warts, *Neisseria gonorrhoeae* [GC], trichomoniasis, and candidiasis). However, even when the analyses were restricted to the 82 cases that did not have any other concurrent STI, vaginal pH remained higher in those cases than in the controls. In univariate analyses, cases were over six times as likely as controls to have a pH >4.5. This study, in itself, was unable to answer whether lower vaginal pH reduces risk of acquisition of urogenital CT infection, and further study is needed. However, the results of this study lead to the hypothesis that reduction of vaginal pH (through treatment) in asymptomatic women with conditions that are known to increase vaginal pH (such as BV), may help to prevent CT infection, particularly in those at increased risk of infection.

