# 2 Study Design

Eight hundred forty-four (844) women, ages 18 to 45, who have had a documented urogenital chlamydia or gonorrhea infection at any time over the 16 weeks preceding the Enrollment Visit, or found to be positive at Screening Visit will be enrolled. A high prevalence of *Chlamydia trachomatis* infection has been observed in those who were treated for urogenital chlamydial infection during the preceding several months. The second infection may result from re-infection through an untreated partner or exposure through a new partner. By including only women who have had a CT infection within the past 16 weeks, this study targets those at high risk for infection (1), (26).

Regardless of whether a potential subject agrees to participate in the study, subjects should be treated according to each site's routine standard of care (SOC) for STI prevention which should follow the prevention strategies recommended by the Centers for Disease Control and Prevention (https://www.cdc.gov/std/tg2015/clinical.htm). These strategies include client-centered STI prevention counseling addressing subject's individual risk factors and advice on the correct and consistent use of male condoms to prevent STIs and human immunodeficiency virus (HIV), as well as condom provision if part of the site's SOC. Those who agree to participate (ie, subjects who provide informed consent) should be treated according to SOC prior to and throughout the study period as necessary.

Subjects will be tested for current GC/CT infection by nucleic acid amplification test (NAAT) via vaginal swab. Those negative for current infection will be enrolled. Those who test positive for CT/GC infection will receive SOC treatment. To meet eligibility criteria, these subjects will not be enrolled until 3 to 4 weeks after screening (at least 21 days after treatment).

Eligible participants will be enrolled and randomized 1:1 (422 subjects per treatment arm) to either AMPHORA or placebo; 5 g of AMPHORA or placebo will be supplied in pre-filled, single-dose applicators. A baseline vaginal pH and a full gynecologic exam (speculum) will be obtained at enrollment.

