#### 5.8.3 Enrollment/Visit 1 (Week $0 \pm 7$ days)

Subjects must be asked to abstain from vaginal intercourse in the 24 hours preceding Study Visit 1. The following will be recorded by research staff in the source documents and CRF:

- 1. Evaluation of inclusion and exclusion criteria
- 2. Evaluation of eligibility criteria
- 3. Demographic data
- 4. Completed Female Sexual Function Index (FSFI) and Sexual Function Questionnaire (SFQ)
- 5. Updated Medical/surgical/gynecologic/sexual history
- 6. Last menstrual period (date, if known)
- 7. Concomitant medication: all medications taken will be recorded in standard data collection forms with attention to drug route, daily dose, duration, start date, stop date and indications
- 8. Body height and weight
- 9. Vital sign measurements (blood pressure, heart rate, temperature)
- 10. Physical exam
- 11. Pregnancy test (urine)
- 12. Vaginal pH\*
- 13. Clinician-collected vaginal swab for CT and GC NAATs
- 14. Gynecologic examination\* (speculum, performed by clinician)
- 15. Randomization and issuance of study product (4-week supply based subject estimation of projected use)
- 16. Instructions on eDiary setup and use

Should subject be menstruating at time of scheduled visit, the visit may be rescheduled during the 7-day visit window, if possible.

Randomization, training, and verification of subject understanding, competency, and willingness to administer study product as directed is documented prior to issuance of study product.

If a subject's CT/GC NAAT results are positive at the enrollment visit, the subject should be immediately terminated from the study, IP accountability conducted, and all used/unused kits

\*Swab for vaginal pH reading is collected prior to introduction of speculum for gynecologic exam.

returned to the clinic. An Early Termination Visit should be performed to complete all procedures indicated for Visit 5 with the exception of repeat GC/CT NAAT testing. The subject should have SOC treatment for the infection and should be encouraged to return for a post-intervention follow-up visit approximately 4 weeks  $\pm 7$  days from Early Termination Visit or last

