#### **Treatment-emergent Adverse Event (TEAE)**

A TEAE is any AE occurring after the application of the study product and within the time of residual product effect, or pre-existing medical condition that worsens in intensity after the application of study product and within the time of residual product effect. The time of residual product effect is 7 days after the dose of the study product, when the effect of the product is still considered to be present based on change of vaginal pH from baseline.

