### 8.1 Study Hypotheses

The hypothesis to be tested in this study is that AMPHORA will prevent the sexual transmission of CT. As noted above, CT infection in women is associated with higher vaginal pH (pH >4.5) (10). This finding is supported by other reports in the literature (7). In addition, a higher vaginal pH has been associated with increased transmission of GC (28). AMPHORA also contains a relatively high concentration of lactic acid (1.8% w/v). Lactobacilli inactivate CT through the production of lactic acid (29). Thus, AMPHORA should reinforce the ability of lactobacilli to maintain healthy levels as well as provide additional lactic acid that may act directly in preventing CT infection.

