#### 8.4 Planned Statistical Methodology

#### 8.4.1 Data Analysis for Efficacy

For the primary analysis, the proportion of subjects who experience at least one CT infection will be compared between the intervention groups (AMPHORA or placebo) using a Chi-square test.

The primary efficacy analysis will be completed using the subjects deemed analyzable (see Section 8.2) from the mITT population.

The primary statistical hypothesis being tested is that there is no difference in the proportion of subjects with CT infections in the AMPHORA intervention group versus placebo. In statistical terms:

$$H0: pAMPHORA = pplacebo, HA: pAMPHORA \neq pplacebo$$

where pAMPHORA and pplacebo denote the proportion of subjects with CT infections during the study while on AMPHORA or placebo, respectively. Denominators for percentages are number of subjects in the mITT population in each intervention group. To test superiority over placebo, the incident infection of CT will be compared against placebo based on a Chi-square test. The estimated difference in proportions, 95% confidence interval, and p-value will be presented. A two-sided 5% type I error rate ( $\alpha$ =0.05) will be used.

Similar analyses will be performed for incident infection of GC.

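### Baseline vaginal pH is measured before randomization and underlies the hypothesis, but no CT comparison in the available text uses it; one pre-specified pH-adjusted risk difference would cost no material power and may add about 0 to 2 points.

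*SAP*

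**What the plan says.** Protocol 8.4.1 has the CT proportions "compared between the intervention groups (AMPHORA or placebo) using a Chi-square test", and SAP 8.8.1 repeats this: "the incidence of infection of CT will be compared against placebo based on a Chi-Square test". Both report the difference in proportions with a 95% confidence interval and p-value, unadjusted.

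Protocol section 2 states: "A baseline vaginal pH and a full gynecologic exam (speculum) will be obtained at enrollment". In the Visit 1 list of Protocol 5.8.3, vaginal pH is item 12, while "Randomization and issuance of study product (4-week supply based subject estimation of projected use" is item 15. The reading therefore comes before allocation and before any gel is issued.

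PH is central to the rationale. Protocol 8.1 argues that "CT infection in women is associated with higher vaginal pH (pH >4.5". Protocol 1.1 cites a case-control study: "In univariate analyses, cases were over six times as likely as controls to have a pH >4.5". The same section concedes that this study "was unable to answer whether lower vaginal pH reduces risk of acquisition of urogenital CT infection". The TEAE definition in Protocol 6.2 also uses pH as its marker of residual product effect, which is "still considered to be present based on change of vaginal pH from baseline".

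In the available SAP text, pH is summarized by visit and arm and listed (8.9.2), and baseline measures in general are tabulated (8.4). The CT analyses in 8.8.1, 8.8.3 and 8.8.4 use visit, adherence, an alternative definition of no re-infection, and condom use. None uses pH. SAP 7.2 was not in the text available for this review, and SAP 1 places the table templates in a separate document, so the point is limited to what could be read.

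**The concern.** The plan collects a covariate that randomization protects and that its own rationale treats as important, but leaves it out of every CT comparison. The covariates it does explore, adherence and condom use, arise after randomization.

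Two things are at stake, both modest. First, planned power is about 80% with little margin, and adjustment for a prognostic baseline value tightens the risk difference. Second, the tables will show any pH imbalance between arms, but no planned analysis shows whether it moved the CT result. For an acid-buffering gel that question is foreseeable, and an adjustment chosen after unblinding would carry little weight.

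**Working it through.** **Inputs from the documents** (Protocol 8.2, SAP 5): 22.5% placebo, 13% AMPHORA, 253 analyzable per arm, two-sided 5%, and losses of 20% + 15% + 5% = 40%.

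**Assumptions, not in the documents:** prevalence q of pH above 4.5 between 10% and 50%; its odds ratio (OR) for incident CT; the amount of missing pH.

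**1. Reproduce the plan.**
- Pooled null SE = √(2 × 0.1775 × 0.8225 / 253) = 0.03397.
- Unpooled SE = √((0.225 × 0.775 + 0.13 × 0.87) / 253) = √(0.287475 / 253) = 0.03371.
- Chi-square power = Φ((0.095 − 1.96 × 0.03397) / 0.03371) = 80.0%.
- Wald power = Φ(0.095 / 0.03371 − 1.96) = Φ(2.818 − 1.96) = 80.5%. This is the like-for-like comparator below.
- 506 / 0.60 = 843.3, rounded up to 844.

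**2. Effect of adjustment.** Take a standardized risk difference from a logistic model with treatment and pH above 4.5 (yes/no), 1:1 allocation. Let d₀ and d₁ be the CT risk differences between high-pH and low-pH women under placebo and AMPHORA, with the overall rates held at 22.5% and 13%. The proportional reduction in large-sample variance is

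r = q(1 − q)(d₀ + d₁)² / (2 × 0.287475),

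and adjusted power is Φ(2.818 / √(1 − r) − 1.96).

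Example, q = 25% and OR 2: placebo risks are 19.2% and 32.3% (d₀ = 0.130); AMPHORA risks are 10.8% and 19.5% (d₁ = 0.087). Then r = 0.1875 × 0.2174² / 0.57495 = 0.0154. Power is Φ(2.840 − 1.96) = 81.1%, a gain of 0.6 points. That equals 253 × (1/(1 − r) − 1) = 4 women per arm.

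| OR for pH above 4.5, both arms | Adjusted power at q = 10 / 25 / 50% | Gain over 80.5% (points) | Women per arm |
|---|---|---|---|
| 1 | 80.5 / 80.5 / 80.5 | 0 | 0 |
| 1.5 | 80.6 / 80.7 / 80.7 | 0.1 to 0.2 | 1 to 2 |
| 2 | 80.8 / 81.1 / 81.1 | 0.3 to 0.6 | 2 to 4 |
| 3 | 81.4 / 82.1 / 82.0 | 1.0 to 1.6 | 6 to 11 |
| 6 | 83.4 / 85.0 / 83.9 | 2.9 to 4.5 | 20 to 33 |

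At q of 30% to 40% the gain is slightly larger: 1.7 points at OR 3. If pH predicts CT only under placebo, the gain is 0.1 to 0.2 points at OR 2, 0.3 to 0.6 at OR 3, and 0.9 to 1.6 at OR 6. The OR 6 row applies only if the case-control figure carried over to incident infection, which the documents do not show.

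**3. Simulation check** (40,000 trials per scenario, 5% of pH missing as its own category). Adjusted type I error was 5.0% to 5.3%, against 4.8% to 5.2% for chi-square. Adjusted interval coverage was 94.5% to 95.0%. Adjusted power was 80.5% to 80.7% at OR 1 and 81.7% to 82.4% at OR 3. About 0.2 points of the simulated advantage over chi-square is Wald versus pooled variance, so the large-sample gains above are the ones to quote.

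**4. Chance imbalance, q = 25%.** The SD of the between-arm difference in prevalence is √(2 × 0.25 × 0.75 / 253) = 3.85 points. The unadjusted difference shifts by the imbalance × (d₀ + d₁)/2; at OR 2 this is 3.85 × 0.109 = 0.4 points. A 1-SD imbalance gives 0.2, 0.4 or 0.7 points at OR 1.5, 2 or 3. A 2-SD imbalance (about 1 trial in 20) gives 0.5, 0.8 or 1.4, against a target of 9.5.

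**5. Missing pH.** Protocol 8.3.3 allows no imputation. If women without pH were dropped, Wald power with 253 × 0.95 or 253 × 0.90 per arm would be 78.4% or 76.2% (simulated: 78.5% and 76.6%). Keeping them in a missing category avoids that loss (simulated: 80.6% and 80.9%).

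**6. Exclusions in SAP 7.3, no CT effect.** In simulation, if GC exclusion depends on pH equally in both arms, type I error stays near 5% for both methods. If it runs through an unmeasured risk factor and differs by arm (20% under placebo, 10% under the gel), both estimates are off by 2.4 points, with type I error of 9.9% (chi-square) and 10.4% (adjusted).

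**The case against.** The strongest reply is that nothing is broken and the gain is small: 1 to 4 women per arm at OR 1.5 to 2, less if the gel flattens the pH gradient. No document figure links enrollment pH to later CT. One reading, taken after a recent infection and followed by 16 weeks of gel use, may predict little. All of this stands, and it is why the point is an improvement and the gain is not assured.

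A second reply is that simulated type I error up to 5.3% and coverage down to 94.5% suggest slight anti-conservatism; power rising to 80.9% with 10% missing and a useless covariate points the same way. That rise should not be read as a gain. A separate check of the null put adjusted type I error within about 0.2 points of the chi-square, which is immaterial.

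Third, at OR 2 a 1-SD imbalance moves the estimate by 0.4 points against a standard error of 3.37, or 0.12 SE, and the unadjusted interval already allows for chance imbalance. This is correct. Adjustment supplies a planned answer and does not rescue an invalid test.

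Fourth, making the adjusted estimate primary displaces the test on which both documents base the sample size, and the cut at 4.5 and the omission of site (the stratification factor) are choices. The displacement is a real cost. The cut is the one Protocol 8.1 names, and omitting site does not invalidate the analysis. A supportive pH-adjusted analysis would still answer the imbalance question, giving up only the small power gain.

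**Conclusion.** The point holds as a worthwhile, low-cost improvement. The chi-square is valid and the plan's 253, 80% and 844 all reproduce. Adjusting for baseline pH leaves large-sample power at 80.5% if pH is not prognostic. It adds about 0 to 2 points for odds ratios up to 3 acting in both arms, or for a six-fold one confined to placebo. A six-fold association in both arms would add about 3 to 4.5 points, so 2 is not a ceiling, but nothing in the documents supports that case for incident infection. These figures rest on assumed pH prevalence and odds ratios. Adjustment does not cure selection from the SAP 7.3 exclusions, which in the scenario shown matters more than anything gained here.

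**What to change.** Before database lock and unblinding, amend SAP 8.8.1 to pre-specify one pH-adjusted analysis on the same CT analysis-eligible mITT set:

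- Fit a logistic model with treatment and baseline pH category (≤4.5, >4.5, missing).
- Average the predicted risks under each arm over all women in the set, and report the standardized risk difference with a robust 95% confidence interval and p-value.
- Name this the primary estimate and keep the unadjusted chi-square as supportive.
- List the change in SAP 9 as a departure from Protocol 8.4.1.
- State that it does not address the SAP 7.3 exclusions.

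The cost is a short paragraph in 8.8.1 and one line in SAP 9. PH is already collected and no extra women are needed. The downsides are that the cut and the missing category must be fixed in advance, the protocol's named test becomes supportive, and the gain is not assured.

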#### 3.7 **Subject Completion**

An enrolled subject will be considered a study completer once any of the following three criterion is met:

- 1. Finishes all study visits without experiencing a urogenital CT or GC infection
- 2. Experiences urogenital CT infection
- 3. Experiences urogenital GC infection

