#### 8.3.3 Procedures for Handling Missing, Unused, and Spurious Data

All analyses will be based on data as observed in the study. No imputations will be performed for data that are missing or spurious.

Given the need to provide treatment to subjects who become infected with CT and/or GC, not all subjects will be evaluable for each endpoint since the use of antibiotics would treat both possible infections. Therefore, the subjects analyzed for the primary efficacy endpoint are those that are infected with CT or who complete the study with no re-infections. Likewise, the subjects analyzed for the secondary efficacy endpoint are those that are infected with GC or who complete the study with no re-infections.

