7.3 Analysis Eligible Subjects

When considering subjects for inclusion in the re-infection analyses, it becomes apparent that some are not appropriate for consideration. As an example, if a subject is treated with an antibiotic for an illness and this antibiotic also treats GC and/or CT, then it is not possible to get a true reflection as to the re-infection prevention abilities of the product under investigation. Likewise, if a subject is found to be infected with GC and needs to be treated, the ability to later detect a CT infection is compromised. As such, for subjects to be eligible for CT (or GC) re-infection analyses, we require the following:

- 1) Known re-infection status through the end of the treatment phase (i.e., a determination of positive or negative re-infection can be definitively made per definitions below),
- 2) No use of prohibited antibiotic medications, and
- 3) No GC (or CT) re-infection, unless it is identified at the same time as the CT (or GC) re-infection.

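### The primary CT analysis counts an infection without a Visit 5 result but a non-infection only with one, so inclusion depends on the outcome and each arm's 16-week risk reads somewhat high if loss is unrelated to CT risk.

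*SAP*

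**What the plan says.** SAP 8.8.1 defines the two outcomes differently. For infection, "any positive NAAT test during the treatment phase (visits 1-5) will constitute re-infection". For non-infection, "a subject with a negative NAAT at visits 1 & 5 with no positive NAATs in between is deemed not re-infected". Women positive at enrolment are already outside the mITT population (SAP 6.2), so the difference in treatment concerns Visits 2 to 4.

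SAP 7.3 makes eligibility for the analysis depend on those definitions: "Known re-infection status through the end of the treatment phase" is its first condition. It also requires no prohibited antibiotic use and, as its third condition, "No GC (or CT) re-infection, unless it is identified at the same time as the CT (or GC) re-infection". SAP 8.8.1 takes the eligible part of mITT as the denominator.

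Protocol 8.3.3 has the same structure: "the subjects analyzed for the primary efficacy endpoint are those that are infected with CT or who complete the study with no re-infections", and "No imputations will be performed for data that are missing or spurious".

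Three planned displays touch the point. SAP 8.8.1 says "tables will be created which also summarize re-infection by each scheduled visit". SAP 8.3 tabulates exclusion reasons by arm. SAP 8.8.3 has an alternative definition of non-infection, which keeps the Visit 5 requirement and adds one more negative visit. SAP 7.2, listed in the contents as the section on missing data, was not available for this review.

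**The concern.** An early positive settles a woman's status for good, but an early negative does not. Women who leave after Visit 2 therefore stay in the analysis if they were already CT-positive and drop out of it if they were not. Each arm loses non-infections selectively.

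The stated endpoint is the proportion of subjects with at least one CT infection in the intervention period. The reported risks, difference and confidence interval would describe only women whose status was settled. The plan expects removals on a large scale: SAP section 5 allows for 20% loss, 15% GC and 5% antibiotic use. If removals differ between arms, the comparison itself can shift as well as the level in each arm.

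**Working it through.** **Plan's own figure.** SAP section 5: 22.5% vs 13%, two-sided 5%, 80% power. With pooled variance,

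n = [1.960 × √(2 × 0.1775 × 0.8225) + 0.842 × √(0.225 × 0.775 + 0.13 × 0.87)]² / 0.095² = (1.059 + 0.451)² / 0.009025 ≈ 253 per arm.

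506 / (1 − 0.40) = 843.3, hence 844. The sample size reproduces and is not in question.

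**Assumptions for the check.** 22.5% and 13% are taken as the true 16-week risks, with a constant CT risk q in each of four 4-week intervals. Loss is unrelated to CT risk, and a woman lost in an interval is not tested at its end. The documents give neither the timing of loss nor its split by arm.

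- q = 1 − (1 − p)^(1/4): 0.0617 placebo, 0.0342 AMPHORA.
- Counted infected = Σ over Visits 2 to 5 of P(first positive at that visit) × P(not yet lost).
- Counted non-infected = (1 − p) × P(never lost).
- Reported risk = infected / (infected + non-infected).

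**Worked case: 20% loss, 5 points per interval.** The fractions not yet lost are 0.95, 0.90, 0.85 and 0.80.

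- Placebo: 0.0617 × 0.95 + 0.0579 × 0.90 + 0.0543 × 0.85 + 0.0510 × 0.80 = 0.1978; non-infected 0.775 × 0.80 = 0.620; risk 0.1978 / 0.8178 = 24.2%.
- AMPHORA: 0.0342 × 0.95 + 0.0330 × 0.90 + 0.0319 × 0.85 + 0.0308 × 0.80 = 0.1140; non-infected 0.87 × 0.80 = 0.696; risk 0.1140 / 0.8100 = 14.1%.

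**By timing, 20% loss in each arm:**

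| Timing of loss | Placebo % | AMPHORA % | Difference | Risk ratio |
|---|---|---|---|---|
| None, or all before Visit 2 | 22.5 | 13.0 | 9.5 | 0.578 |
| Front-loaded (10, 5, 3, 2 points) | 23.5 | 13.6 | 9.9 | 0.580 |
| Even | 24.2 | 14.1 | 10.1 | 0.582 |
| All between Visits 4 and 5 | 25.7 | 15.1 | 10.6 | 0.587 |

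**All planned removals, equal and independent of CT.** Adding 15% GC and 5% antibiotic removal at constant rates gives 26.6% vs 15.7%, difference 10.9, against a standard error of 3.4 points. In simulation the 95% CI covers the true 9.5 in 93.0% of trials (94.6% with loss alone).

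**Unequal loss (AMPHORA/placebo, constant rate).** 25/15 gives 9.3 and 15/25 gives 10.9. With no CT effect (22.5% in both arms), either split gives a spurious 0.9 points, against the arm with more loss, and about 6% rejection.

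**GC removal that differs by arm.** No CT effect, 20% loss, 5% antibiotic removal, GC 15% on placebo and 7.5% on AMPHORA (an assumed halving). A gamma frailty shared by CT and GC represents common exposure. Positive values favour AMPHORA:

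| Frailty variance | SAP rule | Life table |
|---|---|---|
| 0 (independent) | about +1.1 | about 0 |
| 1 | about +0.4 | about −0.5 |
| 2 | about 0 | about −0.8 |
| 3 | about −0.3 to −0.4 | about −1.0 |

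At the planned CT effect with shared risk, the life table reads about 8.3 to 9.2, against a true 9.5.

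**The case against.** The strongest reply has five parts.

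- **The effect is small.** With equal removals the test keeps its level and the risk ratio moves from 0.578 to at most 0.587 under 20% loss. This stands. A reader might infer that the primary test is invalid; with equal removals it is not, and no unequal split is documented.
- **The size depends on timing that the plan does not give.** This stands. A reader might take an overstatement of 0.6 to 1.4 points as following from the planning figures. It does not: it is zero if all loss precedes Visit 2, and the upper end needs GC and antibiotic removals to be independent of CT. SAP section 5 also ties its risks to analyzable subjects, so reading them as true risks is an assumption.
- **GC.** A reader might infer that if AMPHORA reduced GC but not CT, removing GC cases would by itself favour AMPHORA on CT. That holds only if CT and GC risks are close to independent. With strong shared risk the shift vanishes or reverses, and the documents do not settle which applies.
- **Early termination.** Protocol Table 1 puts Visit 5 and early termination in one column and generally requires a NAAT there. If half of the lost women gave a swab that counted as Visit 5, even loss would give 22.1% vs 12.8%, difference 9.3, which is below 9.5. SAP 7.3, Protocol 8.3.3 and the completer definition in Protocol 3.7 ("Finishes all study visits without experiencing a urogenital CT or GC infection") point against counting it, but no visible sentence decides. Half is a high share for women truly lost.
- **SAP 7.2 was not seen.** It is where a missing-data rule would sit, so an omission cannot be asserted.

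None of this removes the dependence of inclusion on outcome. The by-visit tables and exclusion reasons would show an imbalance but yield no corrected difference or interval. The SAP 8.8.3 alternative tightens only the non-infected side.

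**Conclusion.** The concern holds in a limited form. SAP 8.8.1 and 7.3 and Protocol 8.3.3 make inclusion in the primary denominator depend on the outcome. Where loss after Visit 2 is unrelated to CT risk and early-termination swabs do not serve as Visit 5, both arms' 16-week risks are overstated. With equal 20% loss the difference of 9.5 reads 9.5 to 10.6, and about 10.9 if GC and antibiotic removals also act independently. The direction would reverse if lost women carried much higher CT risk than those who stay: about 1.8 times the hazard with even loss.

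The consequence is for estimation first. The test is affected only if removals differ by arm, and then in either direction. If AMPHORA affects GC, GC removal can differ by arm, but the documents do not determine which way that moves the CT comparison. The point is worth fixing before unblinding because the remedy is cheap. Confidence is medium, given the unseen SAP 7.2 and the assumed timing.

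**What to change.** Keep the chi-square test as primary and decisive. Unless SAP 7.2 already provides it, add to SAP 8.8.1 one supportive, pre-specified analysis along these lines:

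> Week-16 CT risk per arm, the difference and its 95% CI (Greenwood variance) will be estimated by life table on the Visit 2 to 5 grid, in mITT subjects with at least one post-baseline NAAT. The event is the first CT-positive NAAT, including CT found together with GC. Other subjects are censored at the last CT-negative NAAT before loss or prohibited antibiotic use, or at the GC-positive visit, whose CT-negative result counts. The chi-square test decides; this analysis is supportive.

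State its limits in the SAP. It corrects for loss unrelated to CT risk: under the assumptions above it returns 22.5% and 13.0%. It does not correct for GC censoring when CT and GC share risk. It is then low at the planned effect (about 8.3 to 9.2 against 9.5), and about 0.5 to 1.1 points against AMPHORA under no CT effect with GC halved.

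For that reason, report first CT-or-GC infection beside it. SAP 2.3 already names this proportion, but only for adherence. It cannot replace the CT result, because its size depends on the GC effect. With independent risks, the difference is 0.775 × 0.85 subtracted from 0.87 × 0.85, or 8.1 points, with no GC effect. It is 0.87 × 0.925 − 0.775 × 0.85, or 14.6 points, with GC halved.

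State whether a negative early-termination NAAT can serve as the Visit 5 negative; in the life table, place it at its actual week. Report by arm how many mITT subjects have no post-baseline NAAT.

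The main cost is an added table and a short SAP text, from NAATs already scheduled. The supportive estimate may be slightly smaller than the primary one. In simulation at the planned effect it disagreed with the chi-square test on significance in 1.3% (loss only) to 3.2% (all removals) of trials, and in 6.3% at 25/15 loss, which is why the SAP must say in advance which result decides.
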